6.0 STUDY MEDICATIONS

6.1 Nivolumab (Anti-PD1, nivolumab)

The vials are not subject specific although there will be specific vial assignments by subject distributed by the Pharmacy in order to track drug usage and re-supply.

6.1.1 Dose Calculation of nivolumab

Nivolumab will be dosed at the the currently FDA-approved dose of 240 mg/dose every two weeks or 480 mg/dose every 4 weeks. The flat dose was recently deemed similar to the 3mg/kg dosing that was previously used. Dose adjustment is not allowed.

6.1.2 Preparation and Dispensing of Nivolumab

The product storage manager should ensure that the study drug is stored in accordance with the environmental conditions (temperature, light, and humidity) as determined by the Investigator Brochure. If concerns regarding the quality or appearance of the study drug arise, do not dispense the study drug and contact the sponsor immediately.

Investigational product documentation must be maintained that includes all processes required to ensure drug is accurately administered. This includes documentation of drug storage, administration and, as applicable, storage temperatures, reconstitution, and use of required processes (e.g. required diluents, administration sets).

Nivolumab vials must be stored at a temperature of 2°C to 8°C and should be protected from light. If stored in a glass front refrigerator, vials should be stored in the carton. Recommended safety measures for preparation and handling of nivolumab include laboratory coats and gloves.

For details on prepared drug storage and use time of nivolumab under room temperature/light and refrigeration, please refer to the Investigator Brochure section for “Recommended Storage and Use Conditions”. Care must be taken to assure sterility of the prepared solution as the product does not contain any anti-microbial preservative or bacteriostatic agent. No incompatibilities between nivolumab and polyolefin bags have been observed.

Nivolumab is to be administered as a 30 +/- 15-minute IV infusion, using a volumetric pump with a 0.2/0.22 micron in-line filter at the protocol-specified dose. The drug can be diluted with 0.9% normal saline or D5W for delivery but the total drug concentration of the solution cannot be below 0.35 mg/ml. It is not to be administered as an IV push or bolus injection. At the end of the infusion, flush the line with a sufficient quantity of normal saline.

6.1.3 Administration of nivolumab

Patients in all two arms (a total of 30 will receive preoperative treatment with nivolumab as a 30 +/- 15-minute IV infusion on Day 1 of a treatment cycle every 2 weeks for arms A and B. Post-surgery adjuvant maintenance nivolumab will be given at 480 mg IV every 4 weeks until disease progression or intolerability. There will be no nivolumab dose escalations or reductions allowed. Patients in each arm may be dosed no less than 12 days from the previous dose. All post-surgical patients may be dosed no less than 12 days from the previous dose. If a subject cannot receive a following dose of the cycle within the designated time frame, it will be omitted and the next dose received will be considered Day 1 of the next cycle.

Nivolumab should be administered under the supervision of a physician experienced in the use of IV agents. Nivolumab is administered as an IV infusion only.

Calculate **Total Infusion Volume** as follows:

$(\text{Total nivolumab dose in mg} \div 10 \text{ mg/mL}) + \text{dilution volume} = \text{total infusion volume in mL}$

Calculate **Total Drug Concentration** as follows:

$\text{Total nivolumab dose in mg} \div \text{Total infusion volume nivolumab dose in ml} = \text{total infusion volume in mg/mL}$.

Total concentration cannot be below 0.35 mg/mL.

Calculate **Rate of Infusion** as follows:

$\text{Total infusion volume in mL} \div 30 \text{ minutes} = \text{rate of infusion in mL/min}$.

Example:

Flat dosing of 240 mg of nivolumab used.

The total infusion volume would be **24 mL** ($240 \text{ mg} \div 10 \text{ mg/mL} = 24 \text{ mL}$) if no dilution volume is added.

The total drug concentration would be **10 mg/mL** ($240 \text{ mg} \div 24 \text{ mL} = 10 \text{ mg/mL}$).

The rate of infusion would be **0.80 mL/min** in 30 minutes ($24 \text{ mL} \div 30 \text{ minutes} = 0.80 \text{ mL/min}$).

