Patients in **Arm A (resectable cohort)** will receive nivolumab at 240 mg IV every 2 weeks for 3 doses followed by liver imaging and hepatic resection on day 1 of week 7, followed (after 4 weeks from surgery) by nivolumab 480 mg IV every 4 weeks in the adjuvant setting until disease progression or for 2 years, whichever is sooner. Patients in **Arm B (resectable cohort)** will receive nivolumab 240 mg IV every 2 weeks for 3 doses plus ipilimumab 1 mg/kg IV on day 1 of therapy (3 doses of nivolumab, 1 dose of ipilimumab) followed by hepatic resection followed (after 4 weeks from surgery) by nivolumab 480 mg IV every 4 weeks plus ipilimumab 1 mg/kg IV every 6 weeks to 4 doses in the adjuvant setting. Adjuvant therapy will start after 4 weeks from surgery with nivolumab 480 mg IV every 4 weeks (Both Arms A and B) plus ipilimumab 1 mg/kg IV every 6 weeks (in Arm B only) for up to 4 doses in the adjuvant setting until disease recurrence or for total of 2 years from first cycle, whichever is sooner. For Arm B, ipilimumab will be administered before nivolumab since the toxicities for ipilimumab are already well-known. Since the doses of nivolumab and ipilimumab either as monotherapy or combination are within maximum tolerated doses as previously defined, no dose increases or reductions will be allowed.

Patients will return at week 6 for a pre-surgical evaluation. A small portion of patients with rapid disease progression (We anticipate 1-3 of a total of 30 patients in Arms A and B) may not have hepatic resection per discretion of the treating surgical and medical oncologists. These patients will be off protocol and treated with other standard or investigational agents. They will be asked to return for an optional biopsy that will be scheduled in place of their surgery. For patients who had significant progression of disease pre-operatively but are still eligible for hepatic resection or transplantation, they will be treated with other investigational agents vs. observation post-operatively as there is no standard adjuvant therapy in surgically resected HCC.

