AFP = alpha fetoprotein; aPTT = activated partial thromboplastin time; Anti-HBc (total) = Total hepatitis B core antibody; Anti-HDV = hepatitis D virus antibody (previously known as 'delta'); anti-HBs = hepatitis B surface antibody; BP = blood pressure; CBC = complete blood count; Discon = discontinuation; ECOG = Eastern Cooperative Oncology Group; FT4 = free thyroxine; HBeAb or anti-HBe = hepatitis B e antibody; HBeAg = hepatitis B e antigen; HBV = hepatitis B virus; HBcAg = hepatitis B core antigen; HBsAb = hepatitis B surface antibody; HBsAg = hepatitis B surface antigen; HCV = hepatitis C virus; HCV Ab = hepatitis C antibody; INR = international normalized ratio; P = pulse; Q12W = every 12 weeks; RR = respiratory rate; T = temperature; PT = prothrombin time; T3 = triiodothyronine; TSH = thyroid-stimulating hormone, ACTH = adrenocorticotropic hormone .

- a. In subjects that experience site-assessed PD or start a new anti-cancer therapy, contact should be made (example; by telephone) q12W to assess for survival status.
- b. Cycle 1 treatment must be given within 3 days of allocation. The window for each visit is ± 3 days until the end of treatment and ± 7 days during follow-up. Nivolumab is given every 4 weeks after surgery.
- c. Height will be measured at Visit 1 only.
- d. For women of reproductive potential, a urine or serum pregnancy test should be performed within 24 hours prior to C1D1, C5D1 and 30 days post treatment. May use screening pregnancy test if performed within 24 hours of first dose. A serum test can be done if urine is not appropriate. Additionally, if urine test is positive or is not evaluable, a serum test is required. Subjects must be excluded/discontinued in the event of a positive test results. Pregnancy tests (serum and/or urine tests) should be repeated if required by local guidelines.
- e. ECOG Performance Status and laboratory tests for screening and determining eligibility are to be performed within 28 days prior to the first dose of trial treatment.
- f. CBC with differential and chemistry to be performed every 2 weeks before surgery. After surgery, CBC with differential and chemistry are performed on every nivolumab administration day.
- g. Urinalysis and thyroid/hormonal function tests will be performed at every cycle before surgery, at time of surgery (C4D1), at C6D1 and at every restaging thereafter (q12 weeks).

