• HBV viral load ^m	X				X		X ^q		X			
• Anti-HBc (total), anti-HBs, and HBe Ag	X											
CENTRAL Laboratory Assessments												
Blood for genetic analysis		X										
Whole blood for biomarker studies (serum and plasma) ^h		X	X	X	X		X ^q		X			
Whole blood for correlative studies (RNA and DNA) ^h		X	X	X	X		X ^q		X			
Tumor tissue collection ^j	X				X							
Efficacy Measurements												
Tumor imaging ^k	X ^{i,n}				X		X ^q		X			

AFP = alpha fetoprotein; aPTT = activated partial thromboplastin time; Anti-HBc (total) = Total hepatitis B core antibody; Anti-HDV = hepatitis D virus antibody (previously known as 'delta'); anti-HBs = hepatitis B surface antibody; BP = blood pressure; CBC = complete blood count; Discon = discontinuation; ECOG = Eastern Cooperative Oncology Group; FT4 = free thyroxine; HBeAb or anti-HBe = hepatitis B e antibody; HBeAg = hepatitis B e antigen; HBV = hepatitis B virus; HBcAg = hepatitis B core antigen; HBsAb = hepatitis B surface antibody; HBsAg = hepatitis B surface antigen; HCV = hepatitis C virus; HCV Ab = hepatitis C antibody; INR = international normalized ratio; P = pulse; Q12W = every 12 weeks; RR = respiratory rate; T = temperature; PT = prothrombin time; T3 = triiodothyronine; TSH = thyroid-stimulating hormone, ACTH = adrenocorticotrophic hormone .

- a. In subjects that experience site-assessed PD or start a new anti-cancer therapy, contact should be made (example; by telephone) q12W to assess for survival status.
- b. Cycle 1 treatment must be given within 3 days of allocation. The window for each visit is ±3 days until the end of treatment and ±7 days during follow-up. Nivolumab is given every 4 weeks after surgery.
- c. Height will be measured at Visit 1 only. Timepoints of directed physical examination will follow nivolumab and ipilimumab administration day.
- d. For women of reproductive potential, a urine or serum pregnancy test should be performed within 24 hours prior to C1D1, C5D1 and 30 days post treatment. May use screening pregnancy test if performed within 24 hours of first dose. A serum test can be done if urine is not appropriate. Additionally, if urine test is positive or is not evaluable, a serum test is required. Subjects must be excluded/discontinued in the event of a positive test results. Pregnancy tests (serum and/or urine tests) should be repeated if required by local guidelines.

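### Section 6.1.3 sets a 12-day minimum interval for post-surgical nivolumab given every 4 weeks, 10 days below the shortest interval the Table 1 visit window allows

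*Combined protocol and SAP*

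**What the plan says.** Section 6.1.3 describes nivolumab in both phases. Before surgery, patients in both arms are dosed every 2 weeks. After surgery the rule is: "Post-surgery adjuvant maintenance nivolumab will be given at 480 mg IV every 4 weeks". Two statements of a minimum interval follow. The first is general: "Patients in each arm may be dosed no less than 12 days from the previous dose". The second is specific to the later phase: "All post-surgical patients may be dosed no less than 12 days from the previous dose". The section then says that a dose which cannot be given in its time frame is omitted, and that the next dose given starts the next cycle.

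The 4-week interval appears consistently elsewhere. Section 6.1.1 lists the two permitted pairings as "240 mg/dose every two weeks or 480 mg/dose every 4 weeks". Section 5.3 gives 480 mg every 4 weeks for adjuvant therapy in both arms. Footnote b to Table 1 says, for each arm, "Nivolumab is given every 4 weeks after surgery", and sets the visit window: "The window for each visit is ±3 days until the end of treatment". The protocol gives no other minimum interval for the 4-week phase.

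**The concern.** A minimum interval exists to stop a dose being given too soon after the last one. For a 14-day cycle, 12 days is a sensible limit. Repeating the same number for a 28-day cycle sets the limit at less than half the intended interval, although the dose has doubled from 240 mg to 480 mg.

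The sentence names post-surgical patients expressly, so someone consulting Section 6.1.3 would take it as the rule for that phase. The practical question is whether it permits anything the schedule does not, and whether it adds any protection beyond the schedule. The stake is dosing safety in the adjuvant phase. No estimate or test in Section 12 depends on it.

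**Working it through.** **Inputs**
- Stated minimum, before and after surgery: 12 days (Section 6.1.3).
- Preoperative cycle: 14 days (Sections 5.3 and 6.1.3).
- Post-surgical cycle: 28 days (Sections 5.3, 6.1.1 and 6.1.3; Table 1 footnote b).
- Visit window on treatment: ±3 days (Table 1 footnote b, both arms); surgery visit ±7 days (Table 1).
- Arm B adjuvant ipilimumab: every 6 weeks, up to 4 doses, starting at Cycle 5 (Table 1, Arm B, footnote r).

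**Formulas.** If visits follow a fixed calendar, the previous dose can be 3 days late and the next 3 days early, so the in-window interval is cycle ± 2 × 3. If the window is counted from an on-time previous dose, it is cycle ± 3. The protocol does not say which applies, so both are shown.

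| Phase | Fixed calendar | From an on-time dose | Effect of a 12-day minimum |
|---|---|---|---|
| Before surgery | 14 ± 6 = 8 to 20 days | 14 ± 3 = 11 to 17 days | Excludes 8 to 11 days (or 11 days) |
| After surgery | 28 ± 6 = 22 to 34 days | 28 ± 3 = 25 to 31 days | Excludes nothing in the window |

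**Shortfall after surgery.** Fixed calendar: 22 − 12 = 10 days. From an on-time dose: 25 − 12 = 13 days. Intervals that meet the Section 6.1.3 minimum but fall short of the Table 1 window are therefore days 12 to 21 (10 values), or days 12 to 24 (13 values).

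**Could 12 days have been meant for something else?**
- *The first adjuvant dose.* The last preoperative dose is due on day 29, surgery on day 43 and the first adjuvant dose on day 71, a gap of 71 − 29 = 42 days. With every window used to shorten it, the gap is (43 − 7 + 28 − 3) − (29 + 3) = 61 − 32 = 29 days. A 12-day minimum does nothing there.
- *Spacing between nivolumab and ipilimumab in Arm B.* Counting from the first adjuvant dose, nivolumab falls on days 0, 28, 56, 84, 112 and 140, and ipilimumab on days 0, 42, 84 and 126. The visits on days 42 and 126 come 14 days after a nivolumab dose, so a 12-day rule could be imagined for them. But the sentence is in the nivolumab section and covers all post-surgical patients, including Arm A, who receive no ipilimumab.

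Neither reading accounts for the figure.

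**The case against.** The strongest reply is that a minimum interval is a necessary condition and not a schedule. The schedule is every 4 weeks ±3 days. It is stated just before the 12-day sentences and again in Sections 5.3 and 6.1.1 and Table 1. A dose given at 28 ± 3 days satisfies every rule, so no two statements conflict, and the rule on omitted doses shows that Section 6.1.3 also relies on the designated time frame. On this view the sentence is slack, not wrong.

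Much of that stands. Early re-dosing is already a deviation under Table 1, and a compliant site will never meet the 12-day limit after surgery. What remains is that an operative dosing rule, addressed by name to this phase, gives a number that does not belong to a 4-week cycle.

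Several stronger readings are tempting, and the documents do not support them:
- *That the protocol authorises 480 mg every 12 days.* That would be 480/12 = 40 mg/day against a planned 480/28 = 17.1 mg/day, or 2.33 times as much. It follows only if the sentence is isolated from the schedule stated around it; nothing shows that such dosing was intended.
- *That the sentence gives no protection at all.* If the window were broken, it would still bar gaps under 12 days.
- *That the number was carried over from the 2-weekly phase.* This is plausible, but it is inference, because the documents do not state its origin.
- *That nivolumab is likely to be given by mistake at the Arm B ipilimumab-only visits.* The 14-day gap is real; the error is speculation.

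**Conclusion.** The point holds at minor severity. The post-surgical minimum of 12 days does not fit 480 mg every 4 weeks. It lies 10 days below the shortest interval the Table 1 window allows, or 13 days below if the window is counted from an on-time dose. The 10-day figure takes the most permissive reading of the window and is therefore the conservative one. It rests on a fixed visit calendar with ±3 days at each visit, an anchor the protocol does not state.

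After surgery the sentence adds nothing to the window and, read alone, permits a dose that Table 1 would class as a deviation. No harm is shown, and no endpoint, sample size or analysis is affected. Enrolment had stopped by January 8, 2020 (Sections 2.0, 5.3 and 12.1), so the benefit is limited to patients still on adjuvant therapy.

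**What to change.** Change the two minimum-interval sentences in Section 6.1.3:
- Limit the 12-day minimum to the preoperative 240 mg doses given every 2 weeks.
- For the post-surgical phase, state that 480 mg doses must be at least 22 days apart and within the Table 1 ±3-day window.

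Use 25 days in place of 22 only if visits are scheduled from the actual previous dose. On a fixed calendar, a 25-day minimum would bar intervals of 22 to 24 days that Table 1 allows. The 22-day figure restates the edge of the window; its purpose is that Section 6.1.3 and Table 1 then give the same answer when read separately.

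The cost is two sentences plus the usual amendment steps in Section 13.1 (ethics board approval and submission to the drug supplier). Visits, data collection and analyses do not change.

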6.1.4 Patient Monitoring During Infusion

Patient vital signs should be monitored prior to dosing, about 15 minutes after initiation of the infusion (then every 15-20 minutes as indicated), at 30 and 60 minutes after completion of the infusion, or longer if indicated, until the vital signs normalize or return to baseline. For subsequent infusions, vital signs should be collected prior to dosing, every 30 minutes during dosing, and 1-hour post dosing. All vital sign time points will be afforded a 10-minute window.

6.1.5 Treatment of nivolumab Related Infusion Reactions

Since nivolumab contains only human immunoglobulin protein sequences, it is unlikely to be immunogenic and induce infusion or hypersensitivity reactions. However, if such a reaction were to occur, it might manifest with fever, chills, rigors, headache, rash, pruritus, arthralgias, hypo- or hypertension, bronchospasm, or other symptoms. All Grade 3 or 4 infusion reactions should be reported within 24 hours to the BMS and reported as an SAE if criteria are met. Infusion reactions should be graded according to NCI CTCAE (version 4.0) guidelines.

Treatment recommendations for nivolumab related infusion reactions are provided below and may be modified based on MD Anderson treatment standards and guidelines, as appropriate:

- **For Grade 1 symptoms** (Mild reaction; infusion interruption not indicated; intervention not indicated):
 - Remain at bedside and monitor subject until recovery from symptoms. The following prophylactic pre-medications are recommended for future infusions: diphenhydramine 50 mg (or equivalent) and/or acetaminophen 325 to 1000 mg at least 30 minutes before additional nivolumab administrations.
- **For Grade 2 symptoms** (Moderate reaction requires therapy or infusion interruption but responds promptly to symptomatic treatment [e.g. antihistamines, non-steroidal anti-inflammatory drugs, narcotics, corticosteroids, bronchodilators, IV fluids]; prophylactic medications indicated for ≤ 24 hours):
 - Stop the nivolumab infusion, begin an IV infusion of normal saline, and treat the subject with diphenhydramine 50 mg IV (or equivalent) and/or acetaminophen 325 to 1000 mg; remain at bedside and monitor subject until resolution of symptoms. Corticosteroid or bronchodilator therapy may also be administered as appropriate. If the infusion is interrupted, then restart the infusion at 50% of the original infusion rate when symptoms resolve; if no further complications ensue after 30 minutes, the rate may be increased to 100% of the original infusion rate. Monitor subject closely. If symptoms recur, then no further nivolumab will be administered at that visit. Administer diphenhydramine 50 mg IV, and remain at bedside and monitor the subject until resolution of symptoms. The amount of study drug infused must be recorded on the case report form (CRF). The following prophylactic premedications are recommended for future infusions: diphenhydramine 50 mg (or equivalent) and/or acetaminophen 325 to 1000 mg should be administered at least 30 minutes before additional nivolumab administrations. If necessary, corticosteroids (recommended dose: up to 25 mg of IV hydrocortisone or equivalent) may be used.
- **For Grade 3 or Grade 4 symptoms** [Severe reaction, Grade 3: prolonged (i.e. not rapidly responsive to symptomatic medication and/or brief interruption of infusion); recurrence of symptoms following initial improvement; hospitalization indicated for other clinical sequelae (e.g. renal impairment, pulmonary infiltrates), Grade 4: life-threatening; pressor or ventilatory support indicated]:
 - Immediately discontinue infusion of nivolumab. Begin an IV infusion of normal saline, and treat the subject as follows: Recommend bronchodilators, epinephrine 0.2 to 1 mg of a 1:1,000 solution for subcutaneous administration or 0.1 to 0.25 mg

of a 1:10,000 solution injected slowly for IV administration, and/or diphenhydramine 50 mg IV with methylprednisolone 100 mg IV (or equivalent), as needed. Subject should be monitored until the investigator is comfortable that the symptoms will not recur. Nivolumab will be permanently discontinued. Institutional guidelines will be followed for the treatment of anaphylaxis. Remain at bedside and monitor subject until recovery from symptoms. In the case of late-occurring hypersensitivity symptoms (e.g. appearance of a localized or generalized pruritus within 1 week after treatment), symptomatic treatment may be given (e.g. oral antihistamine or corticosteroids).

6.2 Ipilimumab (BMS-734016)

Ipilimumab is a human immunoglobulin G (IgG1) κ anti-CTLA-4 monoclonal antibody (mAb). It is supplied in clear, colorless solution at a concentration of 5 mg/ml in 40ml vial.

Ipilimumab (BMS-734016) Injection (5 mg/ml), must be stored refrigerated (2 - 8°C) with protection from light. In preparation of infusion, ipilimumab may be stored in IV infusion bags (PVC, non-PVC/non-DEHP) or glass infusion containers at room temperature or refrigerated (2°C - 8°C) for up to 24 hours. Drug must be completely delivered to the subject within 24 hours of preparation. This includes any time in transit plus the total time for the infusion.

6.3.1 Dose Calculation of Ipilimumab

Total dose should be calculated as in the following example:

Subject's actual body weight in kg x 1 mg = total dose in mg

Therefore, a subject weighing 70 kg who is to receive a dose of 1 mg/kg would be administered 70 mg of ipilimumab (70 kg x 1 mg/kg = 70 mg). Dose adjustment is not allowed.

